Study Title

Study Title: Ertugliflozin: Cardioprotective Effects on Epicardial Fat

NCT Number: NCT04167761

Principal Investigator Contact Information

Name: [name]
Title: Professor of Medicine
Address 1 [name]
Address 2 [name]
City, ST, Zip [name]
E-mail: [contact] (preferred mode of contact)

Institution Contact Information

Name: [name], CT Research Process Manager| Institutional Official
Address 1 Research Management Group
Address 2 Stanford University School of Medicine | [name]
City, ST, Zip
Phone/Fax:
website

Contracting Information (if applicable)

Name: [name]
Phone/Fax: Phone| [contact] Fax| [contact]
E-mail: [contact]

Study Information

Last update: 9/19/2024

Number of Subjects: Goal: 36
61 enrolled (18 for cardiac tissue collection, 43 for bariatric tissue collection), 433 screened (293 for cardiac tissue collection, 140 for bariatric tissue collection)

Key Personnel

1. **[name], MS.** Professor of Medicine, Department of Medicine, Division of Endocrinology, Stanford University School of Medicine. **Role: PI.** Expertise: Clinical/translational research related to diabetes, obesity, metabolism with focus on adipose cell/tissue contributions to metabolic disease. Performed over 1500 fat biopsies from subcutaneous, visceral and epicardial depots. Resources include full access to Clinical Translational Research Unit, offices and computing resources, private wet laboratory, and access to Stanford core laboratory facilities.
2. **[name].** Clinical Professor of Medicine, Department of Medicine, UCLA David Geffen School of Medicine. **Role: Scientific Collaborator.** Expertise: Epicardial fat biology in humans.
3. **[name].** Associate Professor of Surgery, Department of Cardiovascular Surgery. **Role: Cardiothoracic Surgeon.** Expertise: Cardiothoracic surgery.
4. **[name].** Professor of Medicine, Department of Medicine, Division of Endocrinology, Stanford University School of Medicine. **Role: Scientific Collaborator.** Expertise: Fatty acid metabolism/lipolysis.
5. **[name].** Chief of Diabetes and Metabolism (emeritus), NIH/NIDDK. **Role: Scientific Collaborator.** Expertise: adipose cell size measurement and adipose cell biology including insulin-mediated glucose uptake via GLUT4 trafficking.

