Based on prior low carbohydrate diet study, difference to detect between ertugliflozin and control vehicle (mature adipocytes) will be based on differences observed between low and high carbohydrate diets: 0.2 ug FFA release(FFA/ug protein/hour) with SD 0.2, which yields 5 subjects per group for 80% power and alpha 0.05 for unpaired student's t-test (two-tailed). Cell culture with ertugliflozin vs control vehicle: in order to attain statistical power for testing direct actions on EAT from a given subject (comparison of differentiated cells after culture with ertugliflozin vs control vehicle), 8 subjects are needed for similar statistical power using a paired student's t-test. Cell culture with ertugliflozin vs control vehicle: in order to attain statistical power for testing direct actions on VAT and SAT from a given subject (comparison of differentiated cells after culture with ertugliflozin vs control vehicle), 14 subjects are needed for similar statistical power using a paired student's t-test. Measurement of phosphorylated hormone-sensitive lipase (pHSL/HSL ratio reflects HSL activity) will comprise supportive data (in vivo study) for this endpoint and it is expected that ertugliflozin will increase HSL activity, consistent with increased lipolysis.

Secondary endpoint: Inflammatory cytokine expression:

In a prior study ([name] & Engleman, Arteriosclerosis, Thrombosis, and Vascular Biology. 2014;34:2637–2643) in which we measured relative gene expression of inflammatory cytokines in subcutaneous vs visceral fat we found a difference of 1.4 (fold expression) with SD of 1.4, again yielding a number of 5 subjects per group for 80% power and alpha 0.05 for unpaired student's t-test (two-tailed). Cell culture with ertugliflozin vs control vehicle: in order to attain statistical power for testing direct actions on EAT from a given subject (comparison of differentiated cells after culture with ertugliflozin vs control vehicle), 8 subjects are needed for similar statistical power using a paired student's t-test. Cell culture with ertugliflozin vs control vehicle: in order to attain statistical power for testing direct actions on VAT and SAT from a given subject (comparison of differentiated cells after culture with ertugliflozin vs control vehicle), 14 subjects are needed for similar statistical power using a paired student's t-test. Secretome in the supernatant (cell culture and in vivo study) will comprise supportive data.

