Other endpoints including differentiation, FFA uptake and IMGU will be analyzed similarly using unpaired and paired student's t-tests.

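### The unpaired sample size does not follow from its inputs: a difference of one SD needs 17 per group for 80% power, not 5, for both the primary and the secondary endpoint

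*Combined protocol and SAP*

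**What the plan says.** All the sizing is in the Statistical Plans section of the combined protocol and SAP.

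- **Primary endpoint, isoproterenol-stimulated lipolysis.** The difference between ertugliflozin and control vehicle in mature adipocytes is borrowed from an earlier diet study and set at 0.2 (FFA release per unit of protein per hour). The sample size is then stated: "with SD 0.2, which yields 5 subjects per group for 80% power and alpha 0.05 for unpaired student's t-test (two-tailed").
- **Secondary endpoint, inflammatory cytokine expression.** The inputs come from an earlier comparison of fat depots, with the same alpha, test and result: "difference of 1.4 (fold expression) with SD of 1.4, again yielding a number of 5 subjects per group for 80% power".
- **Paired sizes.** Each endpoint also has two within-subject sizes for cultured cells. For EAT: "8 subjects are needed for similar statistical power using a paired student's t-test". For VAT and SAT: "14 subjects are needed for similar statistical power using a paired student's t-test". No SD of the paired differences and no within-donor correlation is stated.
- **Other endpoints.** Differentiation, FFA uptake and IMGU "will be analyzed similarly using unpaired and paired student's t-tests".
- **Enrolment.** Study Information gives a goal of 36 and reports "61 enrolled (18 for cardiac tissue collection, 43 for bariatric tissue collection").

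**The concern.** A difference equal to one SD is a familiar benchmark for the two-sample t-test, and it takes roughly 16 or 17 per group for 80% power. Five is less than a third of that. The unpaired statements are also the only ones in the section that show both inputs and result, so they are the only ones a reader can check, and they fail the check for both endpoints.

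What is at stake is interpretation. A reader who accepts 80% power at 5 per group would take a null unpaired result as fair evidence against an effect of 0.2, when such a comparison would miss that effect about 71% of the time (100% − 28.6%). The paired sizes cannot stand in for the unpaired figure as written, because the quantity that determines them is not given.

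**Working it through.** **Inputs (Statistical Plans).** Primary: difference 0.2, SD 0.2. Secondary: difference 1.4, SD 1.4. Both: two-sided alpha 0.05, 80% power, unpaired t-test, equal groups.

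**Standardised difference.** d = 0.2/0.2 = 1.4/1.4 = 1.0, so one calculation serves both endpoints.

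**Trying to reproduce 5 per group.**

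- Normal approximation: n = 2 × (1.96 + 0.8416)² / d² = 15.7, so 16 per group.
- Exact t-test: noncentral t with 2n − 2 degrees of freedom and noncentrality d × √(n/2). The solution for 80% power is n = 16.71, so 17 per group.

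| n per group | Exact power at d = 1.0 |
|---|---|
| 5 (stated) | 28.6% |
| 16 | 78.1% |
| 17 | 80.7% |

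The stated figure is not reproduced.

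**Other readings of the inputs.**

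| Reading | Needed for 80% power |
|---|---|
| One-sided alpha 0.05 | 14 per group |
| Two-sided alpha 0.10 | 14 per group |
| Two-sided alpha 0.20 | 10 per group |
| Most favourable rounding, 0.25/0.15 = 1.67 | 7 per group (6.76) |
| SD read as that of a between-group difference, d = 1.41 | 9 per group |
| Paired test, SD of differences equal to the difference | 10 pairs (5 pairs give 40.1%) |
| SD read as a variance | 80 (primary) or 13 (secondary) per group |

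Lowering the target to 50% power still needs 9 per group. None of these gives 5.

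**What 5 per group can detect.** Exact power is 80% at d = 2.024. That is 0.2 × 2.024 = 0.405 in lipolysis units and 1.4 × 2.024 = 2.83 in fold expression.

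**What the paired sizes would require.** Assumptions, not in the documents: equal SDs under drug and vehicle, those SDs being 0.2 and 1.4, and a true difference of one SD. Then the standardised paired difference is dz = 1/√(2(1 − ρ)), which gives ρ = 1 − 1/(2·dz²).

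| Pairs | dz for 80% power | Smallest ρ | Largest SD of paired difference, lipolysis | Same, fold expression |
|---|---|---|---|---|
| 8 | 1.156 | 0.63 | 0.2/1.156 = 0.173 | 1.4/1.156 = 1.21 |
| 14 | 0.810 | 0.24 | 0.2/0.810 = 0.247 | 1.4/0.810 = 1.73 |

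**Power at the enrolled numbers, same assumptions.** 18 donors: 80.7% at ρ = 0 and 90.4% at ρ = 0.25. 43 donors: 99.5% at ρ = 0. These are upper figures, because Study Design/Clinical Plan, item 2, notes that EAT samples are small, so some donors may not yield usable tissue.

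**The case against.** The arithmetic is not in dispute. The case on the other side concerns what it matters for.

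*The design is paired, so the unpaired figure is a leftover.* Study Design/Clinical Plan, item 1, says these patients could not take the drug before surgery and were redirected to testing direct effects. Laboratory Methods, item 17, treats pieces of one biopsy with and without drug, and the Treatment section lists only tissue collection for in vitro work. The unpaired calculation, built on a between-diet difference, may well survive from the dropped in vivo comparison. This is a reasonable inference and it limits the consequence. But the text does not mark the calculation as superseded: the sentence names ertugliflozin and control vehicle in mature adipocytes, and unpaired tests are kept for other endpoints.

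*Nothing changes in practice.* The corrected total, 2 × 17 = 34, is within the goal of 36, and 18 cardiac donors supplying both conditions exceed 17 per condition. This stands as a reason not to ask for more donors. It does not make the stated power true.

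*The SD, not the sample size, may be misprinted.* With SDs of half the printed values (d = 2) the requirement is 5.09 per group, so 5 falls just short of 80%. The documents cannot exclude this, but nothing in them supports it either. The sponsor can check the source SDs when making the correction. Until then the printed inputs and result disagree.

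*Eight pairs can be roughly recovered.* If the SD of the paired difference equals the difference, the normal approximation gives (1.96 + 0.8416)² = 7.85, so 8. That is a possible origin of the figure, but the plan does not state that SD. On the exact t-test the same assumption needs 10 pairs, and 8 give 68.1%. Fourteen would give 93.2%, so the one assumption does not explain both sizes.

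**Conclusion.** The concern holds. On the plan's own inputs the unpaired comparison needs 17 per group for each endpoint, and the stated 5 gives 28.6% power instead of 80%. This rests only on figures printed in the Statistical Plans section and the standard t-test power calculation.

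The finding is limited to the written unpaired justification. It does not establish that the within-donor comparisons are underpowered. On the assumptions shown, the enrolled numbers could give adequate paired power. Whether 8 and 14 were adequate targets cannot be judged without a within-donor SD or correlation. The correction is still needed, because it concerns a sample size and power stated for the primary endpoint and repeated for the secondary.

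**What to change.** Correct both statements of 5 per group in the Statistical Plans section, in one of these ways:

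1. State 17 per group for 80% power at the printed difference and SD.
2. Keep 5 per group, but state that it gives about 29% power for the printed difference and detects, with 80% power, about 0.40 in lipolysis units and about 2.8 in fold expression.
3. If the within-donor paired t-test is the governing analysis, say so, drop the unpaired figure, and justify 8 and 14 with a stated within-donor SD or correlation and its source. The sponsor must supply that value.

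The sponsor should check the source SDs at the same time.

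The cost is a wording change, plus one within-donor SD or correlation for each endpoint under option 3. The only drawback is a less favourable stated figure. The correction does not by itself call for more donors, assays or procedures.

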We hypothesize that SGLT2i treatment reduces cardiovascular risk via changes in epicardial adipose tissue (EAT) that yield smaller adipocytes with increased insulin sensitivity, capacity for lipid metabolism (metabolic flexibility) including FFA release via isoproterenol-stimulated lipolysis, which provides fuel for the myocardium during times of increased need, and decreased inflammation, which reduces atherosclerotic plaque and plaque instability.

Study Design/Clinical Plan

- Provide a concise overview stating the type of experimental design

[figure not shown]
1. Test indirect effects of ertugliflozin on EAT: Because ertugliflozin lowers glucose renally, and thus does not invoke insulin secretion, ambient insulin concentrations are lower and FFA higher than other glucose-lowering therapies such as sulfonylureas. Insulin represents a metabolic switch from fasting (low insulin, catabolic, energy releasing) metabolism to fed (high insulin, anabolic, energy storing) metabolism, and the cardiovascular benefits of SGLT2i may be related to a switch in systemic metabolism from high to low insulin state, thereby promoting FFA release from EAT, thereby increasing energy substrate for myocardium, shrinking epicardial adipocytes, enhancing glucose uptake and insulin sensitivity, and decreasing inflammation. Because these patients were unable to take

the drug due to insufficient lead time prior to surgery, we decided to use these patients to test direct effects of ertugliflozin on EAT.

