2. Test direct effects of ertugliflozin on EAT: Harvest fat from epicardial, pericardial, and subcutaneous (chest wall) depots from patients (with or without CAD and with or without type 2 diabetes) undergoing cardiothoracic surgery. Explants of whole tissue and/or collagenase digested mature fat cells will be used to measure lipolysis (basal/isoproterenol-stimulated/insulin-suppressed conditions), secretome (basal conditions only), and gene expression under mock vs drug-treated culture conditions for 2-24 hours¹⁷. In addition, mature adipocytes freshly isolated from collagenase digestion will be obtained from bariatric surgery patients from both SAT and VAT. This is necessary because bariatric samples yield greater quantities of fat for collagenase digestion whereas epicardial fat sample quantities are smaller which necessitates conducting an explant experiment on the tissue. Mature cells from bariatric samples will be tested for lipolysis, insulin-mediated glucose uptake, gene expression, and inflammatory cytokine secretion under mock vs drug-treated culture conditions for 2-24 hours. VAT has many similar qualities to EAT since they are both visceral depots, and thus will augment any results obtained from EAT and provide a mechanism for isolated mature fat cells which otherwise is not possible. In the case of minimal EAT availability from surgical collection, an explant culture will be performed to differentiate stromal vascular cells into the necessary amount of mature fat cells for a lipolysis assay. This experiment addresses the direct effect of ertugliflozin on EAT in the absence of systemic changes such as lower glucose, insulin, and higher FFA concentrations. Due to small amounts of EAT, we will also conduct lipolysis assays on whole tissue explants from all three depots.

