SVCs are pelleted by centrifugation, erythrocytes lysed, and the isolated cells are seeded onto 12-well plates at a density of 10,000 cells per well for assessment of adipogenesis. Adipogenic differentiation medium purchased from Zenbio (Cat#DM2 for subcutaneous depot cells and #OMDM for visceral depot cells) are used to induce differentiation. ERTUGLIFLOZIN and vehicle are supplemented to the adipogenic differentiation medium. At 3 days, medium is changed to maintenance medium from ZenBio (Cat#AM-1) based on the manufacturer's protocol and ertugliflozin is supplemented. Differentiation is carried out for 14 days to achieve terminal differentiation as described^{17,18}.

6) Optimization of ertugliflozin concentration for pre-adipocyte culture studies

SVC are placed in wells with vehicle control and three different concentrations of ERTUGLIFLOZIN (provided by the company). Planned concentrations to test include 10, 100 and 300nmol/L. Media (with or with drug at the listed concentrations)

will be changed every other day with media replenishment. BrdU can be used to determine the proliferation effect at day 3 and day 7. Optimal concentration will be defined as the concentration that yields 50% of growth inhibition.

7) IMGU using 2NDGB method for cultured adipocytes

Assay of Insulin Mediated Glucose Uptake (IMGU) is carried out after 14 days of adipogenic differentiation. On day 14 terminally-differentiated cells are washed with glucose-free PBS three times to remove the residual glucose in the media. Glucose-free PBS is used to fast the cells for additional one hour at 37C. After one hour incubation, 10ug/ml of insulin is added to the cells to stimulate the glucose release, after 10 mins, 100ug/ml of 2-NDBG solution is added to the cells for fluorescence labeling. 30 mins later, cells are washed with PBS twice to remove the residual 2NDBG in the buffer and cells are lysed in the protein lysis buffer (Sigma, Inc). Subsequently, 100ul of lysis are read by excitation/emission=485/535nm to detect the fluorescence incorporation to the cells. The protein lysis concentration are measured by Coomassie Plus™ Protein Assay. Each samples fluorescence reading is normalized by its protein concentration as the final reading. Each assay is set to have three replicates, mean and SD are calculated compared to the control.

8) Total fat uptake using Oil Red O on day 14 of culture

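### Five subjects per group does not give 80% power on the plan's own inputs for either endpoint, and the unpaired test named for mature adipocytes does not fit the culture comparison described

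*Combined protocol and SAP*

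**What the plan says.** All references are to the combined protocol and SAP.

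- **Statistical Plans, primary end point.** The "difference to detect between ertugliflozin and control vehicle (mature adipocytes) will be based on differences observed between low and high carbohydrate diets". The inputs are 0.2 with SD 0.2, "which yields 5 subjects per group for 80% power and alpha 0.05 for unpaired" two-tailed t-test.
- **Same paragraph, differentiated cells.** For ertugliflozin versus vehicle in cells from a given subject, the plan switches to pairing. For EAT, "8 subjects are needed for similar statistical power using a paired" t-test. For VAT and SAT, "14 subjects are needed for similar statistical power using a paired" t-test.
- **Statistical Plans, secondary endpoint.** A difference of 1.4 with SD 1.4, taken from an earlier comparison of fat depots, again leads to 5 per group unpaired. The same paired figures of 8 and 14 follow.
- **Statistical Plans, other endpoints.** These use both unpaired and paired t-tests, and the plan does not say which applies where. Two glucose-uptake assays fall here. The one for cultured cells "is carried out after 14 days of adipogenic differentiation" (Laboratory Methods 7). The other uses freshly isolated mature cells (Laboratory Methods 11).
- **Study Design/Clinical Plan.** Item 1 describes indirect effects, then says patients could not take the drug, so "we decided to use these patients to test direct effects of ertugliflozin on EAT". Item 2 says: "Mature cells from bariatric samples will be tested for lipolysis, insulin-mediated glucose uptake, gene expression, and inflammatory cytokine secretion under mock vs drug-treated" culture conditions.
- **Laboratory Methods 17 and Treatment.** Biopsies are cut into pieces and cultured with and without drug. The Treatment section lists only tissue collection for in vitro work.
- **Study Information.** "61 enrolled (18 for cardiac tissue collection, 43 for bariatric tissue collection").

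**The concern.** There are two linked problems. First, a 1-SD difference is far too small for 5 per group to reach 80% power in a two-tailed unpaired t-test, so the stated justification for the primary and secondary endpoints is wrong arithmetically.

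Second, vehicle is a culture control. If one donor's cells are divided between vehicle and drug, the two readings share that donor's biology and the donor is the natural pairing unit. An unpaired test leaves the between-donor variation in the standard error. With positive correlation its real type I error falls below 5%, its confidence intervals are too wide, and a real direct effect on the primary endpoint can be missed. Adding donors does not remove the miscalibration.

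Because neither test is clearly assigned to mature cells or explants, the test could also be chosen after the results are known.

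**Working it through.** **1. Reproducing the 5 per group.** Inputs from Statistical Plans: 0.2/0.2 = 1 SD (primary), 1.4/1.4 = 1 SD (secondary), two-tailed alpha 0.05, power 80%, equal groups.

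- Normal approximation: n per group = 2 × (1.960 + 0.842)² / 1² = 2 × 7.85 = 15.7, so 16.
- Exact t: 16 per group gives 78.1% and 17 gives 80.7%, so 17.
- Power at 5 per group (df 8, noncentrality 1 × √(5/2) = 1.58): 28.6% by exact t, 35.2% by normal approximation.
- One-sided testing does not rescue it: 42.1% power at 5 per group, 14 per group needed.
- For 5 per group to give 80%, the difference would have to be 2.02 SD. With a difference of 0.2 that means an SD of about 0.099.
- Read as 5 pairs with 0.2 as the SD of differences: 40.1%.

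None of these readings yields 5.

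**2. The plan's paired figures.** If 0.2 is the per-condition SD, the SD of within-donor differences is 0.2 × √(2(1 − ρ)), where ρ is the within-donor correlation. The documents give neither ρ nor an SD of differences.

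| Assumed ρ | Donors for 80% at 1 SD (exact paired t) |
|---|---|
| 0 | 18 |
| 0.24 | 14 |
| 0.5 | 10 |
| 0.7 | 7 |

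The plan's 14 corresponds to ρ of about 0.24. Its 8 is the normal approximation with 0.2 as the SD of differences, which is ρ = 0.5 (7.85, so 8). By exact t, 8 pairs reach 80% only at ρ of about 0.63. So 8 and 14 rest on different, unstated correlations.

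**3. Which test fits.** The unpaired sentence concerns drug versus vehicle in mature adipocytes. Study Design item 2 describes that comparison as mock versus drug-treated culture. No readable passage describes dosing subjects, or one set of donors for drug and another for vehicle. The parallel contrast in differentiated cells is paired. Together these point to within-donor splitting of mature cells, but no sentence states it. For explants, cutting a biopsy and treating pieces with and without drug comes close to stating it, and there the plan names no test.

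**4. Cost of the unpaired test if cells are split.** The true standard error of the mean difference is SD × √(2(1 − ρ)/n). The unpaired test estimates SD × √(2/n). The ratio is 1/√(1 − ρ), whatever n is: 1.15, 1.41 and 1.83 at ρ = 0.24, 0.5 and 0.7.

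The table uses simulation (400,000 datasets per cell) for the unpaired test and noncentral t for the paired test. Here n is the number of donors with both conditions, and the three values in each cell are for assumed ρ = 0.24, 0.5 and 0.7.

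| n | Type I error, unpaired | Power at 1 SD, unpaired vs paired |
|---|---|---|
| 5 | 3.0%, 1.4%, 0.5% | 27 vs 29%, 25 vs 40%, 24 vs 59% |
| 14 | 2.7%, 0.8%, 0.1% | 75 vs 80%, 79 vs 93%, 83 vs 99% |
| 18 | 2.6%, 0.8%, 0.1% | 86 vs 90%, 90 vs 98%, 94 vs >99% |
| 43 | 2.5%, 0.6%, 0.1% | all above 99% |

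If the true effect were half as large (0.5 SD, an assumption), unpaired versus paired power would be:

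- n = 18: 29 vs 37%, 25 vs 52%, 21 vs 73%.
- n = 43: 65 vs 74%, 68 vs 89%, 72 vs 98%.

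At ρ = 0 the paired test loses slightly: 29% falls to 23% at n = 5, and 83% to 81% at n = 18.

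**The case against.** The strongest reply is that the wrong-test claim rests on inference. If different donors supplied the mock and drug-treated mature cells, the unpaired test would be right. The unpaired sentence also takes its inputs from a diet study and speaks of groups, which suits the treated-patient aim in Study Design item 1. Statistical Plans still mentions an in vivo study as supportive data. The sentence may simply be left over, and the paired provision for direct actions on VAT and SAT might be meant to cover mature cells too. This stands in part. It makes the pairing fix conditional. It does not remove the problem, because the sentence names control vehicle and mature adipocytes, the paired provision is worded for differentiated cells, and a leftover sentence would leave mature cells with no named test.

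The practical loss may also be small. With 43 bariatric donors and the plan's 1-SD effect, both tests exceed 99% power. Even 17 per group in separate donors would need only 34. That stands for power at 1 SD, provided enough donors gave usable mature cells, a number the documents do not state. It does not restore the type I error or the interval width.

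The n = 18 rows bear mainly on cardiac explants, since Laboratory Methods 2 limits digestion to VAT and SAT. For explants the plan is silent, not wrong. None of these points touches the arithmetic in step 1.

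**Conclusion.** The sample-size statement is wrong for both endpoints on the plan's own inputs: 28.6% power at 5 per group, with 17 per group needed. This requires no outside assumption.

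The test named for mature adipocytes does not fit the experiment as the readable text describes it. That conclusion is well supported but conditional on each donor's cells being split. Its size depends on ρ, which the documents do not give. At an assumed ρ of 0.5, type I error is about 1.4% at n = 5 and 0.6% to 0.8% at n = 14 to 43. The power loss is negligible at 1 SD with 43 donors, and is 68 vs 89% at an assumed 0.5 SD.

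A reader might infer more than this, and the documents do not support it:

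- **The study is purely in vitro.** Remnants of an in vivo part remain, and the design figure is not available to read.
- **The wrong test is assigned to explants.** None is assigned.
- **The study itself has 29% power.** Enrolment is well above 5 per group.
- **False positives are inflated.** With positive correlation the error runs the other way.

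**What to change.** 1. Delete the claim of 80% power with 5 per group for both endpoints. Restate power for the test actually used, at the number of donors available, over a stated range of within-donor correlation.
2. State whether each donor's mature cells supply both mock and drug conditions. Where they do, name the paired t-test on the within-donor difference for lipolysis, glucose uptake, gene expression and cytokine secretion. Name the same test for explants cut from one biopsy and treated with and without drug.
3. Keep the unpaired test only for named comparisons between different donors. If the present sentence belongs to the dropped in vivo part, say so.
4. Date the change relative to any look at the drug-versus-vehicle data. If data were already seen, label the change post hoc and report both tests, because the paired test will usually reject more often when the correlation is positive. The documents do not say whether analysis has begun.

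The cost is a dated text change, with no new tissue. Donors lacking one condition drop out of the paired test, and power falls slightly if the correlation is near zero, as shown for ρ = 0 above.

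### The paired sample sizes of 8 (EAT) and 14 (VAT and SAT) cannot both follow from the single difference/SD ratio stated for each endpoint, and no depot-specific input is given to explain the gap

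*Combined protocol and SAP*

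**What the plan says.** All the figures are in Statistical Plans of the combined protocol and SAP.

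- **Primary endpoint, isoproterenol-stimulated lipolysis.** The difference is 0.2, "with SD 0.2, which yields 5 subjects per group for 80% power", at two-tailed alpha 0.05 with an unpaired t-test. The values come from a diet study.
- **Secondary endpoint, inflammatory cytokine expression.** A "difference of 1.4 (fold expression) with SD of 1.4, again yielding a number of 5 subjects per group", with the same power, alpha and test. The values come from a comparison of subcutaneous with visceral fat.
- **Paired comparisons, both endpoints.** For EAT, "8 subjects are needed for similar statistical power using a paired student's t-test". For VAT and SAT, "14 subjects are needed for similar statistical power using a paired student's t-test". Both sentences describe the contrast as "comparison of differentiated cells after culture with ertugliflozin vs control vehicle". They differ only in the depot named and the number.

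The section gives no SD of the within-donor difference, no within-donor correlation, no depot-specific effect, no split of alpha and no allowance for lost samples. Power for the paired lines is described only as similar, which I read as the 80% stated just before.

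Study Information reports 18 donors enrolled for cardiac tissue and 43 for bariatric tissue.

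**The concern.** With the same test, the same described contrast and one stated effect per endpoint, a reader expects one paired sample size. The plan gives two, 8 and 14, and says that power is similar at both. Either the inputs differ by depot and were left out, or at least one number is wrong.

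At stake is whether the planned power for the primary endpoint, and for the secondary in the same words, can be reproduced. A reader cannot tell what size of drug effect each depot was meant to detect. A null result in EAT, the tissue the study is about, could therefore not be judged against the plan.

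**Working it through.** **Inputs.** Ratio of difference to SD: 0.2/0.2 = 1.0 and 1.4/1.4 = 1.0. Two-sided alpha 0.05, power 80%. Stated sample sizes: 5 per group unpaired; 8 and 14 paired.

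**Formulas.** Let d be the mean within-donor difference divided by the SD of that difference.

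- Paired t-test: power = P(T > t(0.975, n−1)), with T noncentral t on n−1 degrees of freedom and noncentrality d√n.
- Normal approximation: n = ((1.960 + 0.842)/d)².

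**Step 1: reproduce the plan's paired figures, taking 1.0 as the paired effect (assumption).**

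- Normal approximation: (1.960 + 0.842)² = 7.85, rounded up to 8. This matches the EAT figure.
- Paired t-test: power is 68.1% at n = 8, 80.3% at n = 10 and 93.2% at n = 14. The minimum is 10.
- Neither method gives 14.

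**Step 2: take 1.0 as difference over per-condition SD instead (assumption).** Then d = 1/√(2(1−ρ)), where ρ is the within-donor correlation. By the t-test, 8 is the minimum only for ρ of 0.63 to 0.69, and 14 only for ρ of 0.24 to 0.30. One correlation does not give both.

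**Step 3: drop the stated ratio and ask which effects make each number the minimum.** The paired t-test reaches 80% power at these values of d:

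| n | 7 | 8 | 13 | 14 |
|---|---|---|---|---|
| d | 1.273 | 1.156 | 0.847 | 0.810 |

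So 8 is the minimum for d from 1.156 to 1.273, and 14 for d from 0.810 to 0.847. The ranges do not overlap. They are also separate under the normal approximation (0.99 to 1.06 against 0.75 to 0.78) and under a one-sided t-test (0.98 to 1.07 against 0.70 to 0.73).

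**Step 4: size of the mismatch.**

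- Where 14 is the required number, 8 donors give 51% to 54% power.
- Where 8 is the required number, 14 donors give 98% to 99%.

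**Step 5: what would reconcile the two numbers.**

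- Same difference, unequal variance: the variance of the within-donor difference in VAT/SAT would be (1.156/0.847)² = 1.86 to (1.273/0.810)² = 2.47 times that in EAT.
- Same variance, unequal effect: the VAT/SAT effect would be 0.810/1.273 = 64% to 0.847/1.156 = 73% of that in EAT.
- Smaller alpha, at effects for which 8 is right: 0.025 needs 9 to 10 donors and 0.0125 needs 11 to 12. Reaching 14 takes roughly 0.00625, and then only near the lower end of the range (d about 1.157).

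**Step 6: the unpaired figure on the same inputs.** With noncentrality 1.0 × √(n/2) and 2n−2 degrees of freedom, power is 28.6% at 5 per group, 78.1% at 16 and 80.7% at 17. So 17 per group are needed. Five per group is the minimum only for a standardised difference of 2.02 to 2.38.

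**Step 7: what the enrolled numbers can detect.** The standardised within-donor difference detectable with 80% power is 0.70 at n = 18 and 0.44 at n = 43. With 18 evaluable donors, power at d = 0.810 to 0.847 is 90% to 92%.

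**The case against.** The strongest reply is that unequal numbers for unequal tissues are not a contradiction. Similar power does not mean the same effect, and Study Design/Clinical Plan shows that the material differs: "epicardial fat sample quantities are smaller which necessitates conducting an explant experiment on the tissue", whereas "mature adipocytes freshly isolated from collagenase digestion will be obtained from bariatric surgery patients from both SAT and VAT". Variance or effect could well differ between these formats. This stands, so a reader who infers that 8 and 14 are incompatible in themselves goes too far. What remains is that Statistical Plans states no such difference and describes the powered comparison as differentiated cells in both lines.

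A reader might also infer that 8 has no basis in the stated inputs. That is not so: the normal approximation gives it from the ratio of 1.0. The approximation is too lenient at this size, though, and it is not the test the plan names.

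Nor can one say that no split of alpha could produce 14, since a small enough alpha does. The plan states no split, and dividing alpha by two or four is not enough.

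Finally, enrolment exceeds both numbers, so little hangs on the planning figures in practice. This also stands, and it limits the severity. It does not settle the matter for EAT, because evaluable pairs per depot are not reported and the design section itself foresees scarce EAT.

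**Conclusion.** The point holds as a failure to reproduce the stated sample sizes from the stated inputs. The one ratio given, read as the paired effect, needs 10 donors in every depot under the named test, with 68% power at 8 and 93% at 14. Independently of that reading, no common paired effect makes both 8 and 14 the required number. The same ratio does not support 5 per group unpaired, which gives about 29% power.

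These results assume that similar power means 80% at two-sided alpha 0.05. Because the stated effect and the 5 per group disagree with each other, the documents do not show which input was intended, so I give no replacement sample size.

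A reader might infer that the study is underpowered or should enrol more donors. The documents do not support that: 18 cardiac and 43 bariatric donors exceed both planned numbers. Severity is minor.

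**What to change.** 1. Reconcile 0.2/0.2 and 1.4/1.4 with 5 per group, because every paired figure depends on which is right.
2. For each depot and endpoint, state the expected difference and the SD of the within-donor difference (or the per-condition SD with the assumed correlation), with the source. If the depots are assumed to differ, give the values.
3. Recompute with the paired t-test, and replace the phrase about similar power with the resulting figures.
4. Report evaluable donors per depot and the standardised difference detectable with 80% power: 0.70 if all 18 cardiac donors are evaluable, 0.44 if all 43 bariatric donors are.
5. Say which SAT the figure of 14 covers. The cardiac arm will "Harvest fat from epicardial, pericardial, and subcutaneous (chest wall) depots from patients", while bariatric donors supply SAT as well as VAT.

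The cost is a few sentences and a short calculation, with no change to enrolment or assays. The downside is that the stated power for EAT at 8 may become less favourable, or 14 may prove larger than required, depending on the inputs declared.
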